#### Detailed Procedures:

**Oral glucose tolerance test (OGTT):** An OGTT is the most common clinical procedure to determine impaired glucose tolerance and indices of insulin sensitivity. First, an intravenous catheter will be placed in an arm or hand vein to obtain blood samples for analysis of plasma glucose and glucoregulatory hormones. Blood will be sampled before, 5, 10, 20, 30, 45, 60, 90, and 120 min after completing the consumption of 75 gram glucose beverage. The fasted blood sample will also be used for a blood chemistry panel that includes electrolytes, glucose, in addition to kidney and liver related variables (including creatinine, eGFR, AFR AMER, eGFR, Albumin, Bilirubin, Alk Phos, AST, Uric Acid, ALT, A/G ratio, etc.). Subjects will not be allowed to participate until a medical doctor has signed-off on the blood screening. A 6-week blood draw will be taken to confirm that kidney and liver variables have not changed. Additional blood draws may be obtained per physician discretion.

**Body Composition:** Height, weight will be recorded. Percent body-fat, fat-free mass, total and regional adipose tissue mass, and total bone mineral density will be determined using whole-body dual energy x-ray absorptiometry (DEXA) as we have previously used.

**VO2Max:** Subjects will undergo a 12-lead electrocardiogram (ECG) examination at rest and during a graded exercise test on a stationary bicycle until volitional fatigue, in order to determine maximal oxygen uptake (VO2max). ECG measurements will be made continuously, and blood pressure and ratings of perceived exertion will be recorded. These tests will be performed in the Human Performance/Clinical Research Laboratory (HPCRL) following standard procedures.

**Skeletal Muscle Biopsy:** Skeletal muscle biopsies will be performed using well-established IRB approved SOPs. The belly of the vastus lateralis will be anesthetized locally with 1% lidocaine without epinephrine. A small incision (~4-mm in length) will be made and a Bergstrom needle inserted. Negative pressure will be applied to the inner channel of the needle using a sterile 30-ml plastic syringe. [name]., [name]., or [name] Ph.D. will perform the skeletal muscle biopsies. Collectively, the investigative team has performed this procedure on over 1,000 subjects. A muscle sample will be obtained once before and after the 12-week exercise training (a total of 2 muscle biopsies).

**Exercise Training:** The exercise-training program will be performed within the facilities for the Noon Hour Fitness Program at CSU according to our previously published procedures in older individuals. Exercise will be performed on a treadmill, stationary bicycle, or elliptical and include warm-up (15 min at a heart rate corresponding to 60% of max ) and workout stages (30 min, progression from 65 to 85% of max heart rate by wk 5). The participants will wear heart rate monitors to ensure proper heart rate ranges and the speed, grade or resistance of equipment will be changed to maintain heart rate at the specified percentage of max HR. A CPR trained technician will supervise each exercise session to monitor adherence to the exercise prescription and ensure subject safety. The drinks will be consumed immediately after exercise under supervision.

**Nutritional Intervention:** Subjects will consume either a protein-carbohydrate or carbohydrate drink with a consistency and temperature similar to a smoothie or milk shake immediately after each exercise bout. The protein-carbohydrate drink will be greek yogurt+fruit (~300 kcal, 63g carbohydrate, 20g protein, 1g fat) and the carbohydrate will be fruit (~300 kcal, 82g carbohydrate, 2g protein and 1g fat).

**Metformin and Placebo:** We use a titration dosing protocol in which the amount of metformin starts at 500 mg/day in week 1 and increases by 500 mg/day/week until reaching 2000 mg/day by week 4. 2000 mg/day is the standard clinical dose and used previously by the investigative team. The titration dosing scheme and taking metformin/placebo with meals will help reduce the most common side effects (i.e., gastrointestinal discomfort). If participants experience gastrointestinal discomfort, the dose will be lowered to 1500 mg/day. If participants have a body weight of 75 kg or less the maximal dose will be 1500 mg/day to decrease the risk of gastrointestinal discomfort.

**Stable Isotope Labeling:** The subjects will consume D2O (70%; Cambridge Isotope Laboratories, Andover

MA, USA) during the last four-week period of the 12 week intervention. D2O is a stable, non-radioactive isotope that is indistinguishable from normal water. A target of 1–2% enrichment is achieved during a one-week priming stage (50 ml of D2O 3x/d = 150 ml/d) and maintained for three weeks (50 ml of D2O 2x/d = 100 ml/d) as we have previously performed.

**Optional Continuous Glucose Monitoring (CGM):** CGM is a commonly used device to continuously measure glucose values in healthy control and diabetic populations in both research and clinical applications. Only trained members of the research team will place and remove the CGM devices following a standard operating procedure and user guide. The sensor pod will be secured to the skin of the abdomen using medical grade adhesive. Once secure, a plunger will insert the sensor underneath the skin to record interstitial glucose values every 5 minutes. After careful removal of the applicator, a transmitter will be attached to the secured sensor pod. The transmitter sends data to a receiver. The receiver is smaller than the size of a cell phone to easily fit in a pocket or bag. The receiver needs to be within 20 feet of the device to continuously transmit data. The receiver will be set to blinded mode so the participant will not know their glucose values. The device can be worn up to 10 days. After each 10-day wear a trained member of the research team will remove the sensor. During the 10-day wear the device will prompt the participant to calibrate. After verbal and written instruction, participants will be shown how to perform a finger stick, measure blood glucose using the glucose meter provided and enter the glucose value into the receiver to calibrate the device. During the 10-day wear, participants will be provided a log to record the timing and amount of medications, physical activity, food and drink.

**Optional Physical Activity Behavior Counseling:** After completion of the 12-week exercise intervention, participants will be randomized to 1) receive one session of physical activity behavior counseling (PABC), or 2) no counselling control (CON). The counseling session will consist of strategies based on social-cognitive theory hypothesized to increase physical activity adherence. Session activities will include 1) discussion of the benefits of physical activity, 2) discussion of evidence based recommendations for frequency, intensity, time and type of physical activity for reducing the risk of type 2 diabetes and associated co-morbidities, 3) setting individual physical activity goals, 4) identifying and discussing barriers and facilitators for physical activity, and 5) identifying strategies to overcome barriers. The counseling session will be completed in person while the follow-up questionnaires 12 weeks after completing the exercise training can be done via phone or email.

Healthy participants will complete the medical history questionnaire, resting ECG, graded exercise testing (ECG and VO2max), DEXA, OGTT, CGM, and muscle biopsy.

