**c) Proposed Start Date (may not precede IRB approval date):**

August 1, 2015

2.

Study Procedures (If this is a student project, the methods section of the thesis or dissertation proposal must be attached in section #16 - Attachment section.)

**a) In lay language, describe all the procedures, from screening through end-of-study, that the human subject must undergo in the research project, including study visits, drug treatments, randomization and the procedures that are part of standard of care. Please note: Do NOT respond "See Attachment Section." If you would like to add tables, charts, etc., attach those files in the Attachment section (#16).**

Study Overview:

Pre-diabetic and healthy participants will first undergo a medical questionnaire, resting ECG, graded exercise test with ECG and assessment of VO2max, anthropometric measurement (height, weight and body composition by DEXA scanning), an oral glucose tolerance test (OGTT), and a muscle biopsy.

Prediabetic participants will be screened to eliminate those lactose intolerant, medications known to affect the primary outcomes, medications or recent procedures contraindicated with metformin or not pre-diabetic. Subjects who meet these criteria will be randomized so that subject characteristics are matched between groups, while the study team and participants will remain blinded to treatment (i.e., randomized, double-blind study design). Subjects will be assigned to exercise + carbohydrate + placebo, exercise + protein + placebo, exercise + carbohydrate + metformin, or exercise + protein + metformin.

A minimum of two days apart from the VO2max test, skeletal muscle will be sampled from pre-diabetic and healthy participants. During these visits, pre-diabetic subjects will have the option to participate in a study to test the impact of one counseling session on physical activity after completion of the exercise training and to identify individual, socio-cultural and environmental determinants of physical activity 12 weeks after the end of the exercise intervention. If the subjects wish to participate they will complete questionnaires to measure sociodemographic information, physical activity, self-efficacy, planning, self-regulation and outcome expectancy of exercise, and perceptions of neighborhood support at baseline, completion of exercise training and 12 weeks after the exercise training.

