**\*\*\* Drugs, Reagents, or Chemicals \*\*\***

**7. Drugs, Reagents, or Chemicals**

- a) Please list in the space below all investigational drugs, reagents or chemicals to be administered to subjects during this study.
  
- b) Please list in the space below all commercial drugs, reagents or chemicals to be administered to subjects during this study.

Drug Name	Metformin
Source (e.g., Pharmacy, Sponsor, etc.,)	Pharmacy
If not premixed, where will the material be mixed and by whom	
Manufacturer	
IND # (if available)	
Dosage	Maximum dose of 1500 mg/day
Administration Route	Oral
N	Are these new or different uses of these commercially available drugs, reagents, or chemicals?
N	IND Regulations

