**\*\*\* Subject Population (a-g) \*\*\***

8. Subject Population - In the space below, please detail the participants that you are requesting to recruit (include requested participant number and description of each group requested). (Input N/A if not applicable)
- a) **Requested Participant Description (Include number of participants that you plan to study and description of each group requested, if applicable).**

We plan to recruit 120 men and women with an estimation that 15-25% of participants will not qualify (i.e., screen out) and 15-25% of participants will not complete the study (i.e. drop out). We plan to complete the study in 60 men and women aged >55 years who are prediabetic defined as impaired fasting glucose (100 to 126 mg/dl), HbA1c (5.7-6.4%), family history of type 2 diabetes, and/or impaired glucose tolerance defined as 2 hour postprandial blood glucose of 140 to 200 mg/dl. Participants will be eligible if they meet any 1 of these criteria.

10 healthy individuals, 18-45 years old who have normal glucose values (fasting glucose (<100mg/dl), HbA1c (<5.7%), 2 hour postprandial blood glucose (<140mg/dl)) or no family history of type 2 diabetes will be recruited.

Sub-study: 20 pre diabetic participants and 10 healthy individuals will complete the study.  
Subpopulation of [xx] participants will be recruited for Physical Activity Behavior Counseling (previously approved in Amendment 3.

- b) **What is the rationale for studying the requested group(s) of participants?**

Individuals at risk for T2D are the intended population for metformin; CGM; and Counseling studies. We will use a healthy control group to compare to individuals at risk for T2D.

- c) **If applicable, state the rationale for involvement of potentially vulnerable subjects to be entered into the study, including minors, pregnant women, economically and educationally disadvantaged, or decisionally impaired subjects. Specify the measures being taken to minimize the risks and the chance of harm to the potentially vulnerable subjects.**

We will not enroll minors, pregnant women, economically and educationally disadvantaged, or decisionally impaired subjects.

- d) **If women, minorities, or minors are not included, a clear compelling rationale must be provided. Examples for not including minors: disease does not occur in children; drug or device would interfere with normal growth and development; etc.**

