**Informed Consent**

Title	15-5837H CGM Consent 02242017	
Consent Information Type	Consent	
Sponsor's Consent Version Number: (if any)		
Consent Form Template	X Attachment	15-5837 CGM Informed Consent 24Feb2017 (1)

[Consent Form Samples](http://ricro.colostate.edu/IRB/ConsentAssentTemplates.html)

Who is obtaining consent? The person obtaining consent must be knowledgeable about the study and authorized by the PI to consent human subjects.

How is consent being obtained?

What steps are you taking to determine that potential subjects are competent to participate in the decision-making process?

Title	15-5837H Main Study 24April2017 Stamped	
Consent Information Type	Consent	
Sponsor's Consent Version Number: (if any)		
Consent Form Template	X Attachment	15-5837H Informed Consent 24April2017_Main Study RICRO STAMPED (1)

[Consent Form Samples](http://ricro.colostate.edu/IRB/ConsentAssentTemplates.html)

Who is obtaining consent? The person obtaining consent must be knowledgeable about the study and authorized by the PI to consent human subjects.

How is consent being obtained?

What steps are you taking to determine that potential subjects are competent to participate in the decision-making process?

Title	Healthy Individual Consent 11July2017
Consent Information Type	Consent
Sponsor's Consent Version Number: (if any)	
Consent Form Template	X Attachment 15-5837 Informed Consent Healthy Individuals (1)

[Consent Form Samples](http://ricro.colostate.edu/IRB/ConsentAssentTemplates.html)

Who is obtaining consent? The person obtaining consent must be knowledgeable about the study and authorized by the PI to consent human subjects.

How is consent being obtained?

What steps are you taking to determine that potential subjects are competent to participate in the decision-making process?

---

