**Document Type**

**Investigator's Brochure**

Attachment Document Name	G6 Blinded US_Study Instructions_User Guide G6 Blinded US_Study Instructions_User Guide
Document Type Attachment Document Name	Questionnaire/Survey Participant_Pre Screening 01Sept2016 v.2 Participant_Pre Screening 01Sept2016 v.2
Document Type Attachment Document Name	Recruitment Material (e.g., flyers, email text, verbal scripts) Dairy-Metformin Advertisement Example Dairy-Metformin Advertisement Example
Document Type Attachment Document Name	Recruitment Material (e.g., flyers, email text, verbal scripts) Participant Testimonial Participant Testimonial
Document Type Attachment Document Name	Recruitment Material (e.g., flyers, email text, verbal scripts) new recruitment flyer 1 new recruitment flyer 1
Document Type Attachment Document Name	Recruitment Material (e.g., flyers, email text, verbal scripts) new recruitment flyer 2 new recruitment flyer 2
Document Type Attachment Document Name	Recruitment Material (e.g., flyers, email text, verbal scripts) VIDEO PRODUCTION OUTLINE VIDEO PRODUCTION OUTLINE
Document Type Attachment Document Name	Other Protocol Material GCP protocol v 1.0 7 Decmber2016 v1.0 GCP protocol v 1.0 7 Decmber2016 v1.0
Document Type Attachment Document Name	Other Protocol Material DOA CGM 03Feb2017 DOA CGM 03Feb2017
Document Type Attachment	Grant/Sub-Contract Colorado State University - CTSA IIIS-2016-039 (11-01-2016) (003)

Document Name	Colorado State University - CTSA IIS-2016-039 (11-01-2016) (003)
Document Type	Grant/Sub-Contract
Attachment	CSU Dexcom Proposal 8.4.16
Document Name	CSU Dexcom Proposal 8.4.16
Document Type	Other Protocol Material
Attachment	15.5837H NSR DETERMINATION 02242017
Document Name	15.5837H NSR DETERMINATION 02242017
Document Type	Other Protocol Material
Attachment	15.5837 SR-NSR determination
Document Name	15.5837 SR-NSR determination
Document Type	Other Protocol Material
Attachment	Adverse Event Log 21April2017
Document Name	Adverse Event Log 21April2017
Document Type	Other Protocol Material
Attachment	CGM Adverse Event Log 03Feb2017
Document Name	CGM Adverse Event Log 03Feb2017
Document Type	Other Protocol Material
Attachment	Protocol Deviation CGM applied twice for pre measurements 04April2017 signed

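### Section 7b lists a metformin maximum of 1500 mg/day, but section 2a schedules 2000 mg/day from week 4 for participants above 75 kg who are not reduced for discomfort

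*Combined protocol and SAP*

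**What the plan says.** Section 2a, under Detailed Procedures (Metformin and Placebo), sets out a titration. Metformin starts at 500 mg/day in week 1 and "increases by 500 mg/day/week until reaching 2000 mg/day by week 4". Two exceptions follow. The first is for tolerability: "If participants experience gastrointestinal discomfort, the dose will be lowered to 1500 mg/day". The second is for body weight: "If participants have a body weight of 75 kg or less the maximal dose will be 1500 mg/day". In section 2a, then, 2000 mg/day is the end-point of the titration and 1500 mg/day applies only in those two cases.

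Section 7b, which lists the commercial drugs given to participants, has one entry for metformin. Its dosage field reads "Maximum dose of 1500 mg/day", with no mention of body weight, tolerability or titration.

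The Study Overview in section 2a makes metformin or placebo one of two randomised factors, giving four groups. The Statistical Plan does not mention metformin dose.

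**The concern.** A maximum that applies without condition cannot be lower than a dose that the same protocol schedules. Someone reading section 7b would conclude that nobody in the trial takes more than 1500 mg/day. Someone reading section 2a would conclude that heavier participants who tolerate the drug take 2000 mg/day from week 4. Both are current text in the same ethics application, and both cannot hold for the same people.

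Two things are at stake. First, the maximum dose of a study drug is a safety-relevant figure, and the approved text should state it once. While both figures stand, nobody can judge whether a given participant's dose was within protocol. Second, metformin is an exposure under study: the trial asks whether milk protein offsets a possible blunting of exercise adaptation by metformin. A reader of the results needs to know which dose the metformin groups were meant to take.

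**Working it through.** **Inputs**

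- Starting dose, weekly step and end-point: 500 mg/day, 500 mg/day per week, 2000 mg/day (section 2a, Metformin and Placebo).
- Exceptions at 1500 mg/day: body weight of 75 kg or less, or gastrointestinal discomfort (same place).
- Listed maximum: 1500 mg/day, no condition (section 7b).

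**Step 1: reproduce the titration.** Dose in week w = 500 + 500 × (w − 1), stopping at 2000 mg/day.

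| Week | Section 2a dose (mg/day), no exception | Section 7b maximum (mg/day) | Excess (mg/day) |
|---|---|---|---|
| 1 | 500 | 1500 | none |
| 2 | 1000 | 1500 | none |
| 3 | 1500 | 1500 | none |
| From 4 | 2000 | 1500 | 500 |

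The week-4 figure of 2000 mg/day in section 2a is reproduced.

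**Step 2: size of the gap.** 2000 − 1500 = 500 mg/day, and 500 / 1500 = 33% above the listed maximum.

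**Step 3: who is affected.**

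- Weight of 75 kg or less: section 2a caps the dose at 1500 mg/day, so there is no conflict.
- Reduced to 1500 mg/day for discomfort: no conflict after the reduction.
- Above 75 kg and not reduced: in conflict from week 4.

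**Step 4: possible innocent readings.** Both figures are in mg/day, so units do not explain the gap. The dosage entry in section 7b is a complete phrase, so a gap in the text does not explain it. Neither passage is an amendment log, and the amendment summary at the front of the form describes only a change of principal investigator. Reading section 7b as a summary of section 2a does not work either, because a summary maximum cannot lie below the scheduled end-point.

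**Step 5: how many, for scale only.** Section 8a says "We plan to recruit 120 men and women with an estimation that 15-25% of participants will not qualify". Taking everyone not screened out as randomised gives 120 × 0.75 = 90 to 120 × 0.85 = 102. Assuming equal allocation to the four groups (the documents give no ratio), half take metformin: 90 / 2 = 45 to 102 / 2 = 51. On the planned 60 completers the same assumption gives 60 / 2 = 30. The share above 75 kg and not reduced for discomfort is not given and could be anything from 0 to 100%. The number affected is therefore unknown, and these figures only set an upper bound.

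No cumulative dose is calculated, because the documents give no stop date for metformin.

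**The case against.** The best counter-argument is that this is a clerical slip with little practical risk. The form asks for all procedures, drug treatments included, to be described in section 2a, and that section holds the only operational schedule, with start, step, end-point and exceptions. Section 7b is a single field in a drug table, so staff running the trial would probably work from section 2a. That is plausible, but it is inference: nothing in the supplied text gives one section precedence. It lowers the likely practical consequence and does not remove the contradiction.

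A second argument is timing. The Statistical Plan is written in the past tense, and the event history runs to October 2018 against a proposed start of August 2015. Dosing may have finished, in which case an amendment would change nobody's dose. The documents do not say whether it had. This point stands in part: if dosing is over, a file clarification and a report of the doses actually taken matter more than new protocol wording.

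A third is that documents listed but not supplied might settle the matter, namely the main-study consent ("15-5837H Main Study 24April2017 Stamped") and the attachment titled "GCP protocol v 1.0 7 Decmber2016 v1.0". They may well state a dose. Even so, sections 2a and 7b would still disagree.

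Finally, the headcount is too wide to inform. That is fair, and the conclusion does not rest on it.

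**Conclusion.** The contradiction is real and should be fixed. From week 4, section 2a schedules 500 mg/day (33%) more than the section 7b maximum for metformin participants above 75 kg who have not been reduced for discomfort. The sections are consistent for everyone else and for weeks 1 to 3. This rests only on the two stated doses and the two stated exceptions; no statistical assumption enters.

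The number of participants affected is unknown. This is an internal inconsistency, not a criticism of the dosing design. No view is taken on which figure is right, and no dosing error, safety consequence or bias in the results is claimed. It rates as a must-fix because the figure is the maximum dose of a randomised study drug and the correction is cheap.

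**What to change.** Reconcile the Metformin and Placebo paragraph of section 2a with the dosage entry in section 7b, so that both carry the same maximum, the same titration end-point and the same exceptions. The medical lead must decide the figures. Check that the main-study consent form and the GCP protocol agree with the reconciled text.

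Whatever the stage of the trial, report the dose actually reached in each arm and state which maximum was applied. If dosing has finished, record the clarification in the study file.

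The cost is a short amendment to two sections and a check of two existing documents, plus a table of doses reached. No extra visits or participants are needed.

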Pre diabetic and healthy participants will also have the option to participate in a study to wear a Dexcom generation 6 (G6) continuous glucose monitor (CGM) to measure glucose values every 5 minutes. Healthy participants will wear the device once for up to 10 consecutive days. Pre-diabetic participants will wear the device for up to 10-consecutive days at three different time points: before, during and after the 12-week exercise intervention for a total of 30 days wearing the CGM. The Dexcom G6 CGM is for investigational use only and is not FDA approved. The G6 is modeled after commercially available, FDA approved CGM devices. The differences between the G6 and commercially available devices are a reduced calibration scheme, meaning less finger stick blood glucose measurements for calibration; a longer wear for up to 10 days for the G6 vs. 7 days for commercially available product. Last, commercially available devices could give false high glucose readings if individuals took acetaminophen. The G6 sensor contains updated sensor technology aimed to block the interference of acetaminophen.

After randomization into placebo or metformin groups, the pre-diabetic subjects will begin a 12-wk exercise

intervention consisting of 3 days per week of aerobic exercise training with post-exercise consumption of a 20 gram protein beverage or isocaloric carbohydrate beverage. We have completed this supplementation protocol in previous studies and a currently ongoing investigation.

At the 8-wk time point, pre-diabetic subjects will begin the daily consumption of heavy water (D2O) for the assessment of mitochondrial and individual protein synthesis. At the completion of the training period, the pre-diabetic subjects will repeat all assessments performed prior to training including the DEXA, VO2max, OGTT and muscle sample. Muscle samples obtained pre- and post-training will be used to evaluate mitochondrial function using high-resolution respirometry, western blot analysis, and stable isotope incorporation (post only).

Healthy participants will complete the medical history questionnaire, resting ECG, graded exercise testing (ECG and VO2max), DEXA, OGTT, CGM, and muscle biopsy.

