**Statistical Plan**

Data are presented as mean  $\pm$  standard error of the mean (SEM) and a significance was set a priori at  $P < 0.05$ . Normality was confirmed by the D'Agostino and Pearson test. A two-way ANOVA (Treatment Group x Time) with repeated measures for time was performed. Upon a significant effect, a Holm-Sidak's post-hoc test was used for multiple comparisons. When comparing the change ( $\Delta$ ) from pre to post-intervention between groups, data were analyzed using an unpaired t-test. Pearson's correlation coefficient ( $r$ ) was used to determine associations between dependent variables. GraphPad Prism 7.0 was used to perform statistical analysis

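### The gastrointestinal-discomfort rule does not fit the titration schedule, the 75 kg cap or the maximum dose in section 7, and for participants of 75 kg or less it lowers nothing

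*Combined protocol and SAP*

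**What the plan says.** Four statements in the protocol bear on this.

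- **Titration** (section 2a, Detailed Procedures, Metformin and Placebo): "the amount of metformin starts at 500 mg/day in week 1 and increases by 500 mg/day/week until reaching 2000 mg/day by week 4". The paragraph calls 2000 mg/day the standard clinical dose.
- **Discomfort rule** (same paragraph): "If participants experience gastrointestinal discomfort, the dose will be lowered to 1500 mg/day". It is not limited to a week or a weight class, and no further step is given.
- **Weight cap** (same paragraph): "If participants have a body weight of 75 kg or less the maximal dose will be 1500 mg/day". The stated purpose is to make gastrointestinal discomfort less likely.
- **Drug table** (section 7b): "Maximum dose of 1500 mg/day", with no weight condition.

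The intervention lasts 12 weeks ("the pre-diabetic subjects will begin a 12-wk exercise", completed in the text as an exercise intervention). The Special Precautions answer (section 9e) and the Data Safety Monitoring item (section 9f) give no step for poor tolerance of metformin. The Statistical Plan mentions neither dose taken nor drop-out.

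**The concern.** A tolerability rule should define what happens whenever the symptom can occur. This one names a fixed figure, and that figure is at or above the current dose for much of the treatment period. Titration is when discomfort might first appear, and the lighter group is the one the paragraph singles out for extra caution. In both situations the written response lowers nothing.

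The trial asks whether metformin blunts the adaptation to exercise and whether milk protein offsets that effect. If staff must decide individually what to do about discomfort, or participants leave because no response is defined, the metformin actually taken may differ between participants in ways the protocol does not describe. The plan is for 60 completers with 15-25% drop-out already expected (section 8a), so avoidable losses are unwelcome. Without a record of dose taken, such variation could not be described afterwards.

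**Working it through.** **Inputs.** From the Metformin and Placebo paragraph: start at 500 mg/day, step of 500 mg/day each week, target 2000 mg/day, cap of 1500 mg/day at 75 kg or less, discomfort figure 1500 mg/day. From section 7b: maximum 1500 mg/day. I assume that metformin is taken throughout the 12-week intervention.

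**Reproducing the plan's own figure.** 500 × 4 = 2000 mg/day in week 4, as stated.

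**Formulas.** Scheduled dose in week w = the smaller of 500 × w and the cap. The cap is 2000 above 75 kg and 1500 at 75 kg or less. Gap = 1500 − scheduled dose. Only a negative gap is a reduction.

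| Week | Above 75 kg: dose | Gap | 75 kg or less: dose | Gap |
|---|---|---|---|---|
| 1 | 500 | +1000 | 500 | +1000 |
| 2 | 1000 | +500 | 1000 | +500 |
| 3 | 1500 | 0 | 1500 | 0 |
| 4 to 12 | 2000 | −500 | 1500 | 0 |

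A positive gap means only that the dose cannot be lowered to that figure; it is not an instruction to raise it.

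**Weeks in which the rule lowers the current dose.**

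- Above 75 kg: weeks 4 to 12, which is 12 − 3 = 9 of 12 weeks.
- 75 kg or less: 0 of 12 weeks.

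**Alternative reading: the rule lowers the target, not the current dose.** Above 75 kg, symptoms in weeks 1 to 3 would cancel the later rise, so week 4 onward would be 1500 in place of 2000 (1500 − 2000 = −500 mg/day). The current dose in weeks 1 to 3 would still not fall. At 75 kg or less the target is already 1500, so the change is 1500 − 1500 = 0 in every week.

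**If the section 7 maximum governed.** The cap would be 1500 for everyone, the right-hand columns would apply to all, and the rule would reduce the dose in 0 of 12 weeks for every participant.

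**Number of people affected.** This would be the number on metformin × the share in the relevant weight class or period × the rate of discomfort there. The documents give neither the weight distribution nor the symptom rate, so I give no count.

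**The case against.** The strongest reply is that this is an incomplete rule rather than a contradiction. The discomfort sentence closely follows the statement of the 2000 mg/day target, so the natural reading is that the target is lowered. Heavier participants with early symptoms then have their later rise withheld, and the rule does something. Lighter participants already start under the lower ceiling, so what they lack is a second step. The weight cap makes exposure depend on body weight by design, with or without this rule. Laboratory safety is handled separately, by physician sign-off and a 6-week blood draw for kidney and liver variables (section 2a), and drop-out is allowed for. Section 16 lists a separate GCP protocol and an adverse-event SOP that might give operational instructions.

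Much of this stands. The target reading is plausible, although the text does not state it. It still leaves the rule without effect at 75 kg or less, and without effect on anyone's current dose in weeks 1 to 3. It also does not explain the unconditional maximum in section 7. The attachments were not available; even if they say more, this paragraph and section 7 would have to agree with them.

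Three stronger inferences are tempting, and the documents do not support them.

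- A reader might infer that the rule raises the dose of someone with symptoms in week 1 or 2. The word used is lowered, so the instruction cannot be carried out there; it does not direct an increase.
- A reader might expect sites to differ in how they apply the rule. The Study Location checklist marks a single location.
- A reader might conclude that the metformin-versus-placebo contrast is compromised on every endpoint. Nothing in the documents allows the size of any effect on that contrast to be calculated, and the comparison is randomized and double-blind.

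**Conclusion.** The point holds, at moderate severity. On the protocol's own figures the discomfort rule gives no reduction in any of the 12 weeks to a participant of 75 kg or less, and no reduction of the current dose to anyone in weeks 1 to 3. Above 75 kg it lowers the dose by 500 mg/day from week 4 or, on the target reading, also withholds the later rise after early symptoms. The 1500 mg/day maximum in section 7 conflicts with the 2000 mg/day target; if it governed, the rule would reduce the dose for nobody.

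The likely consequence is ad hoc handling or avoidable drop-out, so that metformin exposure may vary. That is a judgement and has not been measured. A reader might try to count those affected by assuming a share at or below 75 kg. Such a count would have no source in the documents and would include people who never have symptoms. The arithmetic rests only on the stated schedule and caps, and on metformin running for the full 12 weeks.

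**What to change.** The sponsor and the responsible physician should reconcile the titration, discomfort and weight-cap sentences with one another and with the maximum dose in section 7. The result should be a response that can be carried out in both weight classes and during titration. The text should say explicitly that placebo is handled in the same way; the paragraph's heading and the blinding imply this already. The dose actually taken should be recorded, so that exposure can be described by arm. Which dose or rule is right is for them to decide; none is proposed here.

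The cost is one amended paragraph, a matching entry in the section 7 table, aligned instructions for study staff, and a dose record.
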